10.5.3.2 Progression Free Survival

PFS will be summarized using the Kaplan-Meier method. Estimated PFS rates and 95% CIs using complementary log-log transformation method will be presented at 12 and 24 months. The median, 25th, and 75th percentile of PFS and their two-sided 95% CIs using the Brookmeyer-Crowley method will also be presented. Kaplan-Meier curves of the estimated PFS function will also be presented.

This analysis will be performed according to RECIST 1.1 and iRECIST 1.1 in the FAS for both the study phases.

The PFS will be presented in subject-data listing.

10.5.3.3 Duration of Response

DOR per RECIST 1.1 will be summarized with the same approach used for PFS for both the study phases.

The DOR will be presented in subject-data listing.

10.5.3.4 Objective Response Rate

ORR per iRECIST for both the study phases and ORR per RECIST 1.1 for Phase 1 patients in FAS will be summarized with the same approach described in SAP section 12.5.2.2.

The subject-data listing will be provided for tumor assessment and tumor response.

10.5.3.5 Survival rate at 12 and 24 months

The OS will be summarized using the Kaplan-Meier method. Estimated OS rates and 95% CIs using the complementary log-log transformation method will be presented at 12 and 24 months. Median, 25th, and 75th percentile of OS and their 95% CIs using the Brookmeyer-Crowley method will also be presented. Kaplan-Meier curves of the estimated OS function will also be presented.

This analysis will be performed in the FAS of both study phases.

The OS will be presented in subject-data listing.

The analysis of secondary safety endpoints in Phase 2 is detailed in Section 12.7 of the SAP.

The PK and anti-drug antibodies analysis is detailed in Section 12.6 of the SAP.

10.5.4 Exploratory Endpoints

The following exploratory endpoints will be evaluated:

Tumor tissue:

- Expression of immune- and response-related markers such as (but not limited to) PD-L1, CD163, CD68 by IHC.
- mRNA gene signature (transcriptomics/ Nanostring) with special interest in IFN gene signature (PanInflammatory panel and/or IO360 panel).

Peripheral blood:

- Peripheral, soluble ligands and cytokine levels (e.g., IFNγ, TNFα, GM-CSF) contingent on availability of assay (i.e. SIMOA).
- Phenotype and markers of IC activation in peripheral blood (e.g., CD3, CD8, CD4, T_{Regs}, CD4 memory cells, CD25, FOXP3, CD45RA, ICOS, CD14. CD45, CD56, CD19 and ICOSLG) (FACS or ChipCytometry).
- PBMCs gene signature (ribonucleic acid [RNA]) (transcriptomics Nanostring).
- ICOS RO in PBMCs (KY1044 as single agent in Phase 1 only).

All exploratory endpoints will be presented graphically as appropriate.

10.6 Pharmacokinetic and Anti-drug Antibody Analyses

10.6.1 Pharmacokinetic Analyses

The serum PK of KY1044 as a single agent and in combination with atezolizumab will be characterized using non-compartmental analysis (NCA). Nominal times of sample collections will be used for the noncompartmental analysis (NCA). All BLQ values will be set to 0 units.

The following PK measures will be calculated, whenever possible, from serum concentrations:

C_{max}: Maximum concentration (for atezolizumab – only one time point of serum concentration at the end of infusion)

t_{max}: Time of the maximum concentration (obtained without interpolation)

Ctrough: Trough concentrations

 λ_z : Terminal elimination rate constant (whenever possible) using Linear Up Log Down method of determination and Best Fit setting.

AUC_{0-last}: Area under the concentration-time curve calculated using linear trapezoidal summation from time 0 to time last, where "last" is the time of the last measurable concentration

AUC_{0-inf}: Area under the concentration-time curve from 0 to infinity, calculated using the formula: AUC_{0-inf} = AUC_{0-last} + C_{last}/ λ_z , where λ_z is the apparent terminal elimination rate constant

Clearance

Volumes of distribution

t1/2: Half-life

The following diagnostic criteria will be used to flag individual data in Listings:

- %AUCextrap is 30% (criteria for exclusion of parameters: AUCinf, t-half, CL, CLss, Vz, Vss)
- Rsq < 0.7
- half-life calculated over a period of < 2 times the resultant half-life (Span)

For KY1044, all peak (end-of-infusion) and trough (pre-infusion) concentrations will be tabulated. For KY1044 peak and trough concentrations will be tabulated separately for use as a single agent and for combination with atezolizumab.

Besides listings of pharmacokinetic measures for individual patients, all measures will be summarized by descriptive statistics (N, Mean, SD, SE, Min, Median, Max, CV%, and Geometric Mean (only for ratios). The summaries will include estimates of not only central tendency but variability such as Standard Error (SE). For t_{max} median (and range) and for half-lives, arithmetic means will be provided. Besides listings of concentrations, NCA Mean parameter tables, charts illustrating the mean concentration-time profiles will be generated.

10.6.2 Anti-drug Antibody Analysis

The anti-drug antibody analysis will be performed on anti-drug antibody evaluable set.

The anti-drug antibody results will be analyzed descriptively for patients who develop detectable anti-KY1044 and anti-atezolizumab antibodies. The titer of anti-KY1044 and anti-atezolizumab antibodies will be summarized using summary statistics (n, mean, STD, median, minimum and maximum values). The presence of anti-KY1044 and anti-atezolizumab antibodies will be summarized using frequency counts and percentage.

The mean (±STD) plot of titer values of anti-KY1044 and anti- atezolizumab antibodies will be presented.

The summary of anti-KY1044 antibodies incidence will be presented.

The by-subject data listing will be presented.

10.6.3 Biomarker Analysis

The biomarker analysis will be performed on all patients in biomarker evaluable set.

The descriptive summary of change in following marker will be presented:

- number of ICOS positive regulatory T cells (ICOS+FOXP3+) per mm² in the tumor microenvironment.
- number of CD8 positive cells per mm² in the tumor
- number of CD8 positive cells per mm² in the invasive margin
- ratio of CD8 T cells per mm² to the number of ICOS positive regulatory T cells per mm²
- CD8 to Regulatory T-cells ratio
- ChipCytometry Assay

The biomarkers data will be listed in subject data listing.

10.7 Safety Analyses

Unless otherwise specified all safety analysis will be based on safety analysis set.

10.7.1 Adverse Events

AEs will be coded using the MedDRA Version 21.0 or higher.

The analysis described in this section will be based on TEAEs and will be tabulated by SOC and/or PT. The number and percentage of patients experiencing each event at least once will be summarized.

A summary of AEs, including the number of events reported, the number of DLTs reported within 21 days of treatment (Phase 1 only), and the number and percentage of

- patients reporting at least one TEAE by SOC and PT,
- patients with at least one CTCAE grade ≥3 TEAE by SOC and PT,
- patients with at least one TEAE by SOC, PT and maximum CTCAE grade
- patients with at least one TEAE by PT,
- patients with at least one TEAE related to KY1044 by PT,
- patients with at least one TEAE related to KY1044 TEAE by SOC and PT,LLOQ
- patients with at least one TEAE related to Atezolizumab by SOC and PT,
- patients with at least one TEAE related to either study drug by SOC and PT,
- patients with at least one greater than or equal to CTCAE grade 3 TEAE related to KY-1044 by SOC and PT,
- patients with at least one greater than or equal to CTCAE grade 3 TEAE related to Atezolizumab by SOC and PT,
- patients with at least one KY1044-related TEAE by SOC, PT and maximum CTCAE grade,
- patients with at least one Atezolizumab-related TEAE by SOC, PT and maximum CTCAE grade,
- patients with an TEAE leading to study discontinuation of either study drug by SOC and PT,
- patients with an TEAE leading to discontinuation of KY1044 by SOC and PT,
- patients with an TEAE leading to discontinuation of Atezolizumab by SOC and PT,
- patients with an TEAE leading to interruption of KY1044 by SOC and PT,
- patients with an TEAE leading to interruption of Atezolizumab by SOC and PT,
- patients with an TEAE leading to interruption of either study drug by SOC and PT,
- patients with an TEAE leading to reduction of KY1044 by SOC and PT,
- patients with at least one TEAE of special interest by SOC and PT
- patients with at least one irAE by SOC and PT

will be presented. In the summary by worst CTCAE grade, the TEAE with the highest or most severe grade will be counted when patients have multiple TEAEs, overall, in a SOC or in a PT as appropriate.

A breakdown of the number and percentage of patients reporting each kind of TEAE above, categorized by SOC and PT, will be also presented. This breakdown will be sorted by decreasing frequency of PT within SOC. Note that counting will be by subject and not by event and patients are only counted once within each SOC or PT. This breakdown will be repeated and sorted by decreasing frequency of PTs in the KY1044 group for patients reporting at least one TEAE and patients reporting at least one CTCAE grade 3 and above TEAE. This breakdown will also be repeated by worst CTCAE grade for patients reporting at least one TEAE and patients reporting at least one TEAE and patients reporting at least one TEAE.

All adverse events (including non-treatment-emergent events) recorded on the CRF will be listed.

10.7.2 Deaths and Serious Adverse Events

A summary of TEAEs, including the number of events reported, the number and percentage of patients reporting at least one SAE and deaths will be presented.

The following summaries of AEs will be provided for each treatment group by MedDRA primary SOC and PT:

- Serious TEAEs
- Serious TEAEs related to KY1044
- Serious TEAEs related to Atezolizumab
- Serious TEAEs of special interest
- TEAEs with an outcome of death
- TEAEs related to KY1044 with an outcome of death
- Post treatment AEs with an outcome of death

The listings of all SAEs and AEs with outcome of death will be provided. A separate listing of all deaths during treatment will be provided.

10.7.3 Laboratory Data

Actual values, based on central laboratory results, at each planned visit and change in values from baseline at each post-baseline planned visit will be summarized. Nominal visits will be used for these summaries but unscheduled visits will also be considered when looking at potentially clinically important (PCI) results across the entire treatment period.

For parameters that were graded, the worst grade (in the appropriate direction(s)) post-baseline (including from unscheduled assessments) and shifts in grade from baseline to worst will be summarized. All laboratory results over time will be presented in a listing, including reference ranges and indications of out of range values, grading (if done), and an assessment of clinical significance by the Investigator.

Baseline is defined as the last measurement prior to first study drug administration. If the assessment is made on the same day as first study drug administration and there are no times to indicate that it was after administration, it will be assumed to be prior and therefore qualify as the baseline measurement.

Potential Hepatotoxicity will be summarized by time point.

To address the impact of global pandemic of COVID-19, the local laboratory results for all assessment time points will be considered where central laboratory results cannot be obtained. The CRF page "Unscheduled Local Laboratory Results" will be completed in rare circumstances if no central laboratory samples are collected at a visit due to COVID-19 where local laboratory is collected instead. The separate listing will be presented for all local laboratory results obtained from the unscheduled CRF page.

Local laboratory results collected at Screening will be listed separately.

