## Incidence of irAEs across all clinical trials:

Across all clinical trials (n=2616 patients) the incidences of immune-related events were as follows: Infections (42%), colitis/diarrhea (20%), immune related hepatitis (9.0%) hypothyroidism (4.6%), pneumonitis (2.6%), hyperthyroidism (1.6%), infusion reactions (1.3%), adrenal insufficiency (0.4%), type I diabetes mellitus (<0.1%) and hypophysitis (<0.1%), (atezolizumab label [43]).

Other clinically significant immune-related adverse reactions were reported in  $\leq 1.0\%$  of patients:

Cardiac: myocarditis.

Dermatologic: bullous dermatitis, pemphigoid, erythema multiforme, Stevens Johnson Syndrome (SJS)/toxic epidermal necrolysis (TEN).

Gastrointestinal: pancreatitis, including increases in serum amylase or lipase levels.

General: systemic inflammatory response syndrome, histiocytic necrotizing lymphadenitis.

Hematological: autoimmune hemolytic anemia, immune thrombocytopenic purpura.

Musculoskeletal: myositis, rhabdomyolysis. Neurological: Guillain-Barre syndrome, myasthenia syndrome/myasthenia gravis, demyelination, immune-related meningoencephalitis, aseptic meningitis, encephalitis, facial and abducens nerve paresis, polymyalgia rheumatica, autoimmune neuropathy, and Vogt-Koyanagi-Harada syndrome.

Ophthalmological: uveitis, iritis.

Renal: nephrotic syndrome, nephritis.

Vascular: vasculitis.

Overall the incidence of AEs leading to discontinuations was small and was reported for pneumonitis and hepatitis in 0.4% of patients, and for diarrhea and colitis in 0.2% of patients.

Summary Benefit: Risk Statement

Although potential benefits of KY1044 as single agent or in combination with atezolizumab in advanced/metastatic malignancies are unknown at this time, the study design aims to minimize potential risks for patients and will try to maximize clinical benefit. In all late stage tumor indications, and in the preferred tumor indications, there is a high unmet medical need for novel therapeutic agents and improvement of efficacy over currently approved treatments.

There are precedents for an antibody against ICOS with dual MoA (for example, JTX-2011). Although patient numbers are limited, the reported Phase 1/2 data investigating JTX-2011 as single agent and in combination with nivolumab seem to have been well tolerated (47, 48).

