#### Amended Clinical Trial Protocol 07 KY1044/SAR445256-KY1044-CT01/TCD17370 - alomfilimab

10-Nov-2021 Version number: 1

		• If central hypothyroidism, replace thyroid hormone (see above) after corticosteroids have been initiated	
Note: In	the uncommon scenario of MRI fi	ndings without pituitary deficiency, consider high dose corticosteroids for prevention of hormonal dysfunc	tion.
* Hypop	ohysitis is not defined in CTCAE V	ersion 4.0. This classification is drawn from the CTCAE category 'Endocrine disorders - Other'.	
Hypoth	yroidism		
Grade	CTCAE description	Management	Specialist referral?
1	Asymptomatic; clinical or	
 
Hold ICI for ≥Grade 3 irAEs
 
	1
	diagnostic observations only; intervention not indicated	• ICI can be continued after resolution of symptoms to Grade 2 or better.	
2	Symptomatic; thyroid replacement indicated; limiting instrumental ADL	• Start standard thyroid replacement therapy: initial dose can be the full dose (1.6 mcg/kg) in young, healthy patients, but a reduced dose of 25-50 mcg should be initiated in elderly patients with known cardiovascular disease.	
3	Severe symptoms; limiting self-care ADL; hospitalization	• Repeat TSH and free T4 testing after 6-8 weeks and adjust thyroid hormone dose accordingly. If TSH is above reference range, increase thyroid hormone dose by 12.5 mcg to 25 mcg	
4	Life-threatening consequences;	• After identification of the appropriate maintenance dose, further evaluation is required every year, or sooner if patient's status changes	
	urgent intervention indicated	• After identification of the appropriate maintenance dose, further evaluation is required every year, or sooner if patient's status changes	
Hypert	ıyroidism		
Grade	CTCAE description	Management	Specialist referral?
1	Asymptomatic; clinical or	• Hold ICI for ≥Grade 3 irAEs	1
	diagnostic observations only; intervention not indicated	Standard therapy for hyperthyroidism should be followed	
2	Symptomatic; thyroid	• Thyroiditis is self-limiting and has 2 phases:	
	suppression therapy indicated; limiting instrumental ADL	
 
In the hyperthyroid phase, patients may benefit from beta blockers if symptomatic (eg, atenolol 25-50 mg daily, titrate for HR <90 bpm if BP allows). Monitor closely with regular symptom
 
	
3	Severe symptoms; limiting self-care ADL; hospitalization indicated	evaluation and free T4 testing every 2 weeks.	

Property of the Sanofi Group - strictly confidential

PAGE 74 OF 217

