- a After receiving the first infusion in Phase 1, patients will be either hospitalized or remain in the clinic for at least 6 to 8 hours until the last assessments. They will be provided with instructions for after hour care as per institutional standard and will return to the clinic on C1D2. Patients should remain in the clinic for at least 3 hours at all other visits where infusions are given.
- b IXRS contact can be performed prior to the patient's CXD1 visit to receive treatment allocation.
- c Medical History including date of diagnosis and dates and extent of cancer, prior antineoplastic therapies (chemotherapies, targeted agents, radiation, surgery) and current concomitant medication (including SARS-CoV-2 vaccines).
- *d* Complete physical examination should be performed at screening and at the EOT. This should also include a full dermatological examination (complete skin and mucosal exam). Abbreviated physical examination will be performed every cycle (see Section 6.5.2).
- e Vital signs: during Cycles 1 and 2, blood pressure (BP) and HR will be monitored in the clinic every 15 minutes during the infusions of study treatment and every 30 minutes inbetween the infusions (for combination therapy) and 60 min after the last infusion of study treatment and before the patients are discharged from the hospital on Cycle 1 Day 2. See Section 6.5.7.
- f Cardiac markers at screening will include: Baseline Troponin I for all patients. Additionally, N-terminal pro B-type natriuretic peptide (NT-pro-BNP) will only be taken for patients with a history of cardiac disease (according to exclusion criteria). Repeated assessments of cardiac markers during the study will be performed only when clinically indicated .
- g ECGs will be taken pre- and post-dose at Cycles 1, 3 and 6 as close as possible to the relevant PK timepoints (see Section 6.5.8). In the event of abnormal ECG findings and if clinically indicated, an unscheduled PK sample should be collected and Troponin I, together with assessments for CK, CK-MB, AST and lactate dehydrogenase (LDH). NT-pro-BNP should be measured together with the other cardiac markers as outlined above only in patients with previous cardiac complications at screening.
- h All samples will be analyzed centrally. On the occasions marked h only, duplicate samples for immediate access to key safety laboratory parameters (hematology, clinical chemistry and coagulation) will be analyzed at local labs as well.

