- *i* At screening, clinical chemistry includes collection of a fasting lipid profile sample.
- j HbA1c should be measured every 12 weeks throughout the study and will be assessed at EOT only if the previous assessment has not been performed within the last 3 months.
- k Serum pregnancy test ( $\beta$ -HCG) will be performed at screening. Urine dipstick test will be performed at all other visits.
- 1 Thyroid function includes free T4 and TSH and the analyses will be repeated every 3 cycles and at EOT.
- *m* Virology testing will be performed at screening for HIV, HBV and HCV. In patients, who are known to be positive for HBV and HCV, tests will be repeated every cycle pre-dose and a confirmatory sample should be taken when clinically indicated. See Section 6.5.9 for more details.
- *n* Auto-antibodies include: anti-DNA, anti-nuclear, anti-mitochondrial and anti-phospholipid antibodies and Rheumatoid factor (RF) and acetyl-choline receptor antibodies (AChR). When a blood sample is positive for ANA (ie, titer >40) it will be tested for antibodies against extractable nuclear antigens. Samples for auto-antibody analyses will be collected at screening, every second cycle pre-dose for the first six cycles (C2, C4, C6), then every 12 weeks up to 48 months of treatment, when clinically indicated and at EOT.
- 0 ADA samples should be collected at every cycle at pre-dose on Day 1 and unscheduled at any time, when clinically indicated. For detailed ADA sample collection schedule see Section 6.4.2.
- p PK samples will be taken pre- and post-dose during all cycles and unscheduled at any time, when clinically indicated. For detailed PK analysis timings please refer to Section 6.4.2. Note: On days and timepoints when biomarker and pharmacokinetic blood samples are being collected, the PK sample must be drawn first. For further details please see schedule
- of PK assessments in Section 6.4.2 and biomarker assessments in Section 6.3.1.
   q In patients with measurable disease, a fresh tumor biopsy should be taken once other screening investigations strongly suggest the patient is likely to be eligible, to avoid unnecessary risk of biopsy for a patient who is not going to be eligible. Where a prior (archival) biopsy is available that is less than 3 months old this may be substituted for a fresh tumor biopsy at screening. A

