#### 6.5.6 Safety Laboratory Tests

All laboratory parameters assessed will be evaluated centrally. However, laboratory tests for safety evaluation, such as hematology, clinical chemistry and coagulation parameters will also be assessed locally at indicated times during each cycle. In exceptional circumstances, the use of local labs may also be considered for assessment of screening laboratory values, after approval by the medical monitor.

Refer to the Schedule of Assessments (Table 6-1, Table 6-2 and Table 6-8) for a summary of the parameters to be evaluated.

More frequent evaluations may be performed at the Investigator's discretion if medically indicated; results should be recorded as unscheduled laboratory assessments.

Laboratory tests will be performed as described below and according to the schedule of assessments.

- All laboratory reports should be reviewed, signed and dated by Investigators. Any clinically significant changes will be recorded as AEs.
- Any single laboratory abnormality without clinical signs or symptoms needs to be repeated before qualifying as an AE.
- All clinically relevant abnormal laboratory tests occurring during the study may be repeated at appropriate intervals until they return to baseline or to a level deemed acceptable by the Investigator or until the abnormality is explained by an appropriate diagnosis.

Full details relating to the methodology of analysis, sample processing, labelling, storage, shipment and destruction procedures will be documented in a laboratory manual.

Test category	Test name	Time of assessment	Approx. mL
			per cycle
			(central assessment
			omy)
Phase 1 and 2 (unl	ess otherwise specified)	I	
Hematology	
 
Hematocrit (HCT), Hemoglobin (Hgb), Reticulocytes, red blood cell count (RBCC), mean cell hemoglobin (MCH), mean hemoglobin concentration (MCHC) and mean cell volume (MCV)
 
Platelets
 
White blood cells with Differential (Basophils, Eosinophils, Lymphocytes, Monocytes, Neutrophils)
 
	
 
Screening a,
 
C 1 b: D1 pre-dose, D2 c, D8, D15
 
C 2 b: D1 pre-dose, D8, D15
 
C 3 b: D1 pre-dose, D8
 
From Cycle 4 b: Day 1 pre-dose (CxD1)
 
EOT
 
	2 mL/sample 2 mL = Screening 8 mL = C1 6 mL = C2 4 mL = C3 2 mL = C4 -EOT
	• HbA1c	
 
Screening a
 
Every 12 weeks: pre-dose (C5D1 etc.).
 
EOT d
 
	

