#### 9.4.3 Safety Analysis

The Phase 1 primary and Phase 2 secondary safety endpoints include:

- Safety: Incidence and severity of AEs and SAEs, including changes in laboratory parameters, vital signs and ECGs
- Tolerability: Dose interruptions, reductions and dose intensity

For Phase 1, the primary endpoints will also include:

- The incidence of DLTs with KY1044 as single agent during the first 21 days of treatment
- The incidence of DLTs with KY1044 in combination with atezolizumab during the first 21 days of treatment

All AEs in the clinical trial database will be coded according to the Medical Dictionary for Regulatory Activities (MedDRA) Version 21.0 or higher, which will be used to summarize AEs by primary system organ class (SOC) and preferred term (PT). All AEs will be displayed in listings.

A treatment emergent adverse event (TEAE) is defined as an AE observed after starting administration of the specific treatment. If a patient experiences an event both prior to and after starting administration of a treatment, the event will be considered a TEAE (of the treatment) only if it has worsened in severity (ie, it is reported with a new start date) after starting administration of the specific treatment, and prior to the start of another treatment, if any. All TEAEs collected during the investigational period will be summarized.

Treatment-related AEs/SAEs coded by primary SOC and PT will be summarized in those receiving at least one infusion of KY1044.

Additional summaries by severity of AEs/SAEs will also be produced.

Actual and change from baseline data for vital signs and ECG parameters will be reported using summary statistics.

When relevant, for laboratory variables, descriptive statistics for results and changes from baseline will be provided during the on-treatment period. These analyses will be performed using local measurements for laboratory variables. Clinical laboratory results will be graded according to NCI CTCAE version 5.0, when applicable. Number (%) of participants with laboratory abnormalities (all grades and by grade) using the worst grade during on-treatment period will be provided for the all-treated population.

When the NCI CTCAE version 5.0 scale is not applicable, the number of participants with laboratory abnormality out-of-normal laboratory range value will be displayed.

The number of dose interruption, reductions and incidence of DLTs will be summarized.

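### Protocol 9.4.3 takes laboratory summaries from local results and SAP 10.7.3 takes them from central results without recording the change; the SAP also omits the protocol's out-of-range patient count

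*SAP*

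**What the plan says.** **Source of the data.** Protocol 9.4.3 plans descriptive statistics for on-treatment laboratory results and their changes from baseline, then adds: "These analyses will be performed using local measurements for laboratory variables". SAP 10.7.3 plans the same two summaries but starts from "Actual values, based on central laboratory results, at each planned visit". It admits local results only where a central result could not be obtained because of COVID-19.

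**Tests that cannot be graded.** For tests outside the CTCAE v5.0 scale, Protocol 9.4.3 commits that "the number of participants with laboratory abnormality out-of-normal laboratory range value will be displayed". SAP 10.7.3 tabulates worst grade and grade shifts for graded parameters only. Out-of-range values otherwise appear as a flag in the listing. The section also mentions looking at PCI results over the whole treatment period, but gives no limits, parameters or table.

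**What is collected.** Protocol 6.5.6 has every parameter measured centrally. Local measurement is additional and limited. Under Table 6-1, footnote h, on marked occasions only, "duplicate samples for immediate access to key safety laboratory parameters (hematology, clinical chemistry and coagulation) will be analyzed at local labs as well". Table 6-2 has the same rule for Phase 2, and Table 6-8 attaches its local-laboratory footnote to the same three panels. For thyroid tests the schedule is: "Thyroid function includes free T4 and TSH and the analyses will be repeated every 3 cycles and at EOT".

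**The concern.** Laboratory change is part of the Phase 1 primary safety endpoint and of the Phase 2 secondary safety endpoint. Two current documents give a programmer opposite instructions on which results feed the tables, and neither acknowledges the other. A reader who checks the study report against the protocol would find an unexplained deviation.

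The missing count matters for a different reason. Means by visit can hide a few patients who drift out of range, and a listing leaves the reader to count them. Adverse event tables do not fully replace the count, because Protocol 6.5.6 states: "Any single laboratory abnormality without clinical signs or symptoms needs to be repeated before qualifying as an AE". A symptom-free abnormal value that is seen once and not repeated can therefore stay out of the adverse event tables. The SAP does plan abnormality summaries for vital signs (10.7.4) and QTcF (10.7.5.2), so the gap is particular to laboratory data.

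**Working it through.** The plan gives no figure to reproduce. The check is a comparison of texts and a count of scheduled samples.

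**Step 1: do the two source rules cover the same analyses?** Yes. In Protocol 9.4.3 the local-measurement sentence directly follows the sentence on results and changes from baseline. SAP 10.7.3 opens with actual values and changes from baseline. These are the same summaries with opposite sources.

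**Step 2: is the difference recorded?** No. The SAP Introduction says the plan was developed using protocol version 7.0 and that changes will be tracked in the Document History. The version 3.0 entry there lists the safety set, best overall response, the PK section and the template. The version 2.0 entry aligns the SAP with protocol version 6.0. No entry concerns the laboratory source. The protocol's summary of changes shows that text was added to Section 9.4.3 in version 7.0, so carried-over SAP text is a plausible cause, although the documents do not say so.

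**Step 3: can the local rule be carried out?** Inputs: Protocol Tables 6-1, 6-2 and 6-8, and about 70 cycles at most (Protocol 3.4).

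- *TSH and free T4.* Draws are at screening, on Day 1 of Cycles 3, 6, 9 and so on, and at EOT. None is marked for a local duplicate.
  - Post-baseline central draws after *n* cycles = floor(*n*/3) + 1, where the 1 is EOT.
  - *n* = 1 or 2: 0 + 1 = 1. *n* = 3 to 5: 1 + 1 = 2. *n* = 6 to 8: 2 + 1 = 3.
  - *n* = 70: 23 + 1 = 24, and with screening 25.
  - Scheduled local draws: 0 in every case.
- *Auto-antibodies.* They are drawn at screening, Cycles 2, 4 and 6, every 12 weeks thereafter and at EOT, with no local mark. Scheduled local results: 0. Urinalysis carries no local mark either.
- *Hematology, chemistry, coagulation.* Local duplicates are marked at treatment-cycle visits but not at EOT. If EOT is a separate visit, the central series has one more scheduled result per panel than the local series. Under Protocol 8.2 a regular visit may become the EOT visit. If that visit is marked for duplicates, the difference is 0.

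**Step 4: is the out-of-range count specified anywhere?**

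| | Count of out-of-range participants for ungraded tests | Source named for it |
|---|---|---|
| Protocol 9.4.3 | Yes | None in that sentence |
| SAP 10.7.3 | None; listing flag and undefined PCI review | Not applicable |

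**The case against.** The case for leaving the plan alone has several parts.

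*The SAP governs.* Protocol 9.4 leaves full analysis detail to the SAP, which is the later document and already uses the workable source. This stands as a reason to prefer central. It does not excuse the silence: a SAP that departs from the protocol should say so. The protocol's opening qualifier, that descriptive statistics are given when relevant, does not change the source it names.

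*The count can still be produced.* A reader might infer that neither document yields an out-of-range count for thyroid tests. The text does not support that. The protocol's out-of-range sentence stands in a later paragraph and names no laboratory, so it can be read as using the central data that the SAP adopts. What remains true is that the SAP specifies no such output.

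*Thyroid tests may not be ungraded.* Table 5-5 grades hypothyroidism by clinical state, for example Grade 2 as "Symptomatic; thyroid replacement indicated; limiting instrumental ADL", which suggests that TSH and free T4 have no value grade. But it is a toxicity-management table and the documents never state this outright. The omitted count concerns any ungraded test, so the point does not depend on this example.

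*Clinical cases are captured elsewhere.* A reader might take the atezolizumab thyroid event rates in Protocol 1.6.4 as a measure of cases that would be lost. They are not. They are event incidences, and reported events enter the planned adverse event, special-interest and immune-related tables in SAP 10.7.1. Protocol 6.5.6 also records clinically significant changes as adverse events and allows abnormal tests to be repeated, and Protocol 5.6.2 sets follow-up after a stop or interruption for a clinically significant value. The count would add only the isolated, symptom-free abnormalities that these routes may miss.

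**Conclusion.** The point holds as a minor inconsistency with one omitted output. The two documents name different laboratory sources for the same summaries, and the SAP does not record the difference. The local rule has no scheduled data for thyroid tests (0 local against up to 25 central draws per patient) or for auto-antibodies. For the three duplicated panels the shortfall is at most one scheduled result per patient, at EOT, and it can be zero. It should not be read as a fixed percentage loss.

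The SAP omits the protocol's participant count for tests outside CTCAE v5.0, and its PCI review is too undefined to stand in for it.

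This rests on the printed schedule. Unscheduled local results, local screening results allowed by exception and COVID-19 substitutes may exist, but they are not a planned series. No dose or expansion decision depends on these tables, so the consequence is limited to the completeness and traceability of safety reporting.

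**What to change.** In SAP 10.7.3, name central results as the source for all laboratory summaries, with a local result used only where the central one is missing. State there, and in the Document History, that this changes Protocol 9.4.3.

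Add one table: for each test without a CTCAE v5.0 grade, the number and percentage of safety-set patients with any post-baseline value outside the normal range, unscheduled values included. Confirm the list of ungraded tests against CTCAE v5.0 before programming, starting with TSH and free T4.

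The cost is one sentence and one standard table. No new data are needed, because central results, reference ranges and out-of-range flags are already in the planned listing. The SAP already provides for a final version to be approved before database lock.
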